**Table 2. Baseline assessment in the PERCePT trial**

Potential covariate(s)	Instrument(s)	Explanation and estimated completion time
Patient characteristics	PERCePT study case report forms TIGAR-O 	
 
• Data will be collected as applicable and available: history of acute pancreatitis episodes, date of chronic pancreatitis diagnosis, duct and parenchyma characteristics on prior imaging, anthropomorphic data, chronic pancreatitis risk factors (TIGAR-O)
 
• 5-minutes
 

Harmful alcohol drinking	Alcohol Use Disorders Test (AUDIT) 	
 
• Screening instrument for hazardous and harmful alcohol drinking
 
• 2-minutes
 

Current pain disability	RAPID 	
 
• Pain-related disability (90-day recall); developed, validated,
 

		
and used for the EPISOD study
 
 
• 3-minutes
 

Average daily pain, mood, activity-level, sleep and analgesic medication use	Ecological Momentary Assessment (EMA)	
 
• Ecological daily diaries designed to capture repeated measures of average daily pain using an 11-point Numeric Rating Scale
 
• Repeated measures of activity level, sleep, and use of opioid medications
 
• Assessed from day -14 to day 0
 

Pain Severity and Functional Impairment	Brief Pain Inventory (BPI)	
 
• Measures pain at its worst, least, average, and at time of evaluation
 
• Measures patient perception of effectiveness of current pain medications
 
• Measures functional impairment due to pain
 
• 7-minutes
 

Pain Character	PROMIS Pain Quality - Neuropathic and Nociceptive	
 
• Assessment of pain quality
 
• 5-minutes
 

Pain Catastrophizing	Pain Catastrophizing Scale (PCS)	
 
• Measurement of negative cognitive-set brought to bear during painful experiences
 
• Predictor of functional impairment due to pain and pain-related depression
 
• 5-minutes
 

Quality of life	PROMIS 29 Profile	
 
• Assessment of anxiety, depression, fatigue, pain interference, physical function, sleep disturbance, ability to participate in social roles and activities, and a single pain intensity item
 
• 5-minutes
 

Somatization	Brief Symptom Inventory – 18 (BSI-18)**	
 
• Assessment of psychological distress and somatization
 
• 5-minutes
 

Patient expectation of response	Questions Before ERCP-Endotherapy	
 
• Quantitative measure of the degree to which a patient expects to improve after pancreatic endotherapy
 
• 1-minute
 

Opioid utilization	
 
- Current Opioid Misuse Measure (COMM)
 
- Baseline Opioid Medication For Abdominal Pain Form
 
	
 
• Self-report measures of risk for aberrant medication-related behavior in patients prescribed opioids for chronic pain
 
• 3-minutes
 

Laboratory Pain and Central Sensitization	Quantitative Sensory Testing (QST)	
 
• Thermal and mechanical pain threshold, pain tolerance, as well as wind-up and conditioned modulation testing to assess central pain facilitation and inhibition
 
• 1-hour baseline visit
 

**The study investigator or their staff will respond to any subjects presenting suicidal ideations by using standard psychiatric procedures for safety purposes. If the BSI -18 Question 17 is answered low (1-2), the Coordinator will refer the subject to a mental health specialist for follow up. If the risk is considered moderate to high (3-4), the Coordinator will page the PI or a clinician and seek guidance for possible admission to mental health services without leaving the subject alone.
		

### 10.1.3 Follow-up visits, day 0 -90

The subject will be contacted by telephone at day 7 and 30, and complete the Ecological Momentary Assessment during this 30-day period. After the 30 day follow up phone call is complete, the participant will be compensated \$50 for their time. Thereafter, follow-up will

be on an as-needed basis until the subject returns on day 90 for the first formal follow-up assessment (details in *table 3*). The discussion regarding next steps in treatment will occur between the subject, a blinded gastroenterologist, and a blinded hepatobiliary surgeon. A multidisciplinary discussion between patient, endoscopist, and surgeon complies with society guidelines. In the case of medical management, this will be directed by the blinded physicians. In the event of an emergency room or inpatient hospitalization due to abdominal pain or other symptoms potentially attributable to chronic pancreatitis, a blinded physician will determine whether repeat endoscopic or surgical intervention is warranted before the 90-day outcome assessment. In the event that the patient is referred for repeat endoscopic or surgical intervention before reaching the 90-day outcome assessment, the Ecological Momentary Assessment tool will be reactivated in order to capture pain data for up to 14 days leading up to and including the day of intervention, as feasible. Rather than assuming no change from baseline in pain scores for those that have a re intervention prior to day 90, we will capture the pain score prior to re intervention and use these data to calculate the change score for the primary analysis.

The day 90 follow-up assessment will include completion of selected instruments and a discussion with blinded physician investigators about their clinical course. It is not realistic to assign a threshold pain score above which further intervention should be offered, so it is expected that the blinded physicians and patient will decide whether an intervention is required to treat pain; this highlights the importance of the study's sham design. Potential scenarios are detailed in *figure 2*. Although not incorporated into this study's pilot primary outcome, it is expected that a decision to proceed with an intervention to treat pain would be considered a "failure" of pancreatic endotherapy in a definitive clinical trial. Each of the groups in figure 2 are explained in further detail below. The design of the hierarchical diagram is deliberate and intends to illustrate that management options for groups 3 and 4 are the same. In addition, follow-up is in part dependent on the original treatment allocation. So, after all blinded assessments have been completed and a decision regarding intervention determined, an unblinded investigator will need to advise the subject regarding next steps. Participants will be compensated \$75 after completing the 90-day follow up visit. If participants complete all visits, they will be compensated a total of \$200.

**1. Sham group, no intervention advised.** In this scenario, the subject is doing well enough that no intervention is advised. Since no procedures have been performed until this point, continued medical management is reasonable. The subject would be followed through day 360 for relevant changes in clinical course and to assess secondary endpoints.

[figure not shown]
**2. Endotherapy group, no intervention advised.** In this scenario, the subject is doing well enough that no intervention is advised. Since pancreatic endotherapy had been performed during the randomization procedure, the subject would be advised to undergo repeat pancreatic endotherapy to remove pancreatic duct stents. In some cases, the treating endoscopist may recommend replacing or upsizing stents in an effort to minimize stricture recurrence. This will be determined by the unblinded treating physician per standard of care. Follow-up procedures would be open-label, although it is possible that the subject remain blinded to their original treatment allocation.

**3. Sham group, intervention advised.** In this scenario, the subject is doing poorly, and an intervention is advised. The blinded physicians will discuss three options with the patient: 1) further medical management, including the initiation or titration of analgesics; 2) pancreatic endotherapy; 3) consideration of surgical interventions.

**4. Endotherapy group, intervention advised.** In this scenario, the subject is doing poorly, and an intervention is advised. The blinded physician investigator will discuss three options

with the patient: 1) further medical management, including the initiation or titration of analgesics; 2) pancreatic endotherapy; 3) consideration of surgical interventions. Since the subject had previously undergone pancreatic endotherapy, the unblinded physician investigator will need to be informed of the recommendation and proceed endoscopy to remove pancreatic duct stents if necessary and applicable.

All procedures performed during the day 90 visit and thereafter will be open-label and are within the spectrum of routine clinical procedures.

**Figure 2. Potential scenarios during the 90-day follow-up visit**

#### 10.1.4 Follow-up visits, day 91-360

Every effort will be made to preserve the integrity of the original treatment allocation, recognizing the need for a pragmatic approach to the follow up period. Although 90-day outcomes will be the focus of this pilot study, all subjects will be followed for 12 months after randomization at which point the same outcome measures will be assessed. These data will be used to examine changes in the 90-day and 12-month outcomes, recognizing that interventions performed after 90 days will be unblinded.

The content of follow-up visits at days 180, 270, and 360 are detailed in **table 3** and may be completed by telephone or in-person.

**Table 3. Follow-up assessments in the PERCePT trial**

Outcome measures	Instrument(s)	Follow-up visit				Explanation and estimated completion time
		90	180	270	360	
Clinical evaluation	Blinded physician evaluation	X				
 
Assessment by a blinded gastroenterologist and pancreatobiliary surgeon
 

Patient characteristics	PERCePT study follow-up case report forms	X	X	X	X	
 
Data will be collected as applicable and available: history of acute pancreatitis episodes, opioid utilization, interventions performed and hospital encounters during the interval follow-up period
 
5-minutes
 

Harmful alcohol drinking	Alcohol Use Disorders Test	X	X	X	X	
 
Screening instrument for hazardous and harmful alcohol drinking
 

	(AUDIT) 					
 
• 2-minutes
 

Current pain disability	RAPID 	X			X	
 
• Pain-related disability (90-day recall); developed, validated, and used for the EPISOD study
 
• 3-minutes
 

Average daily pain, mood, activity-level, sleep and analgesic medication use	Ecological Momentary Assessment (EMA)	X				
 
• Electronic daily diaries designed to capture repeated measures of pain, activity, sleep, and opioid use
 
• Daily from days 0-30 and 76-90
 

Pain Severity and Functional Impairment	Brief Pain Inventory (BPI)	X	X	X	X	
 
• Measures pain at its worst, least, average, and at time of evaluation
 
• Measures patient perception of effectiveness of current pain medications
 
• Measures functional impairment due to pain
 
• 7-minutes
 

Quality of life	PROMIS 29 Profile	X	X	X	X	
 
• Assessment of anxiety, depression, fatigue, pain interference, physical function, sleep disturbance, ability to participate in social roles and activities, and a single pain intensity item
 
• 5-minutes
 

Laboratory Pain and Central Sensitization	Quantitative Sensory Testing (QST)	X				
 
• Thermal and mechanical pain threshold, pain tolerance, as well as wind-up and conditioned modulation testing to assess central pain facilitation and inhibition
 
• 1-hour follow-up visit
 

Opioid Utilization	Current Opioid Misuse Measure (COMM)	X	X	X	X	
 
• Self-report measures of risk for aberrant medication-related behavior in patients prescribed opioids for chronic pain
 
• 3-minutes
 

Pain Catastrophizing	Pain Catastrophizing Scale (PCS)	X	X	X	X	
 
• Measurement of negative cognitive-set brought to bear during painful experiences
 
• Predictor of functional impairment due to pain and pain-related depression
 
• 5-minutes
 

Patient Global Impression of Change	PGIC	X	X	X	X	
 
• Patient's assessment of efficacy from the index ERCP procedure
 
• 1 minute
 

## 11.0 Data Management

### 11.1 Data Monitoring Plan

*The below applies to the PERCePT pilot trial and subsequent multicenter, definitive trial, as applicable.*

The purpose of clinical trial monitoring is to ensure that: 1) the rights and well-being of human subjects are protected; 2) trial data are accurate, complete, and verifiable from source documents; and, 3) the trial is conducted in compliance with the current approved protocol, with GCP, and applicable regulatory requirements. In accordance with the FDA's "Guidance for Industry Oversight of Clinical Investigations — A Risk-Based Approach to Monitoring", the study team will adopt a dynamic approach to data monitoring, which focuses on critical risks and utilizes centralized monitoring, and on-site site monitoring to increase data quality, maximize efficiency, reduce

redundancy, and better utilize monitoring resources. The DCU which is serving as the statistical and data management center for the proposed trial are highly experienced in providing centralized and risk-based monitoring for clinical trials. As data are submitted by the enrolling site during the course of the study, the data manager carefully reviews the data for errors or omissions within or across forms. Meanwhile, the study statistician carefully reviews the eCRF data in aggregate and across CRFs to identify errors and trends. As errors are identified by the data manager and statistician, the data manager generates Data Clarification Requests (DCRs) to the site using the DCU's clinical trials management system, referred to as WebDCU™. Critical or systemic errors identified by central monitoring are shared with study team members so that swift and appropriate action can be taken including the development of a corrective action plan when needed.

The DCU's risk-based monitoring approach is based upon the premise that a certain level of random error in non-critical data is acceptable and that efforts should be focused on decreasing errors in data associated with the planned analysis and human subject protection. The level of risk is affected by factors including study design, study endpoints, study population, experience of investigators, data collection methods, safety profile of an investigational product/intervention, stage of the study, and quantity of data. Prior to the start of the study, the study team will identify the risks associated with the trial. This monitoring plan is then developed to most effectively mitigate these critical risks, if the source of risk cannot be eliminated entirely.

**11.2 Sample Size.** A total of 30 subjects will be randomized (15 per arm) within a 21-month period. In a recent retrospective cohort study including patients undergoing first-time pancreatic endotherapy for chronic pancreatitis at the Medical University of South Carolina, the average number of new patients/year undergoing pancreatic endotherapy was 22, and > 30 in recent years. This is above our estimated enrollment rate for this pilot study.

**11.3 Data Management.** Paper files will be stored in locked filing cabinets in restricted access offices at OHSU and MUSC. All clinical data on enrolled subjects will be data entered by study personnel into a web-based clinical trials management system, WebDCU, which is managed by the Data Coordination Unit (DCU), Department of Public Health Sciences at MUSC. This user friendly, secure web-based database system, developed by the DCU, will be used for subject randomization, data entry, data validation, project progress monitoring, subject tracking, user customizable report generation and secure data transfer. Access to data will be restricted to study personnel. All study team members will receive a unique user account and ability to set up their own private password. The system has an audit trail to track all logins and enter/edit of study data.

De-identified data from the study will be stored indefinitely. In the event of a screen failure of a consented subject, data collected during screening will be retained for separate analysis.

**11.4 Statistical Analysis.** The analysis will be conducted according to the intention-to-treat (ITT) principle wherein subjects will be analyzed according to the assigned treatment. Several exploratory analyses and descriptive statistics will be examined, including covariates. Secondary analyses of additional outcomes, including change in QOL scores, disability, and depression, will be approached in a similar manner and considered exploratory using confident intervals rather than p values.

**11.5 Data Security and Confidentiality.** During the course of the trial, user access to the files with subject identifiers, and the files with study outcomes will be restricted to core staff with any exceptions to be approved by the Executive Committee. In addition to use of passwords and other security measures, all documents containing identifying information on individuals or physicians are considered confidential materials and will be safeguarded to the greatest possible extent. No information, which identifies a specific person, hospital, or physician, will be released to, or discussed with anyone other than study staff members.

**11.6 Quality Control.** Upon entry of CRFs into the study database, quality control procedures will be applied at each stage of data handling in order to ensure compliance with GCP guidelines, integrity of the study data, and document processing system reliability. The site will be monitored by the DCU and the site monitor will conduct periodic site visits to review source documents and case report form information. A quality assurance record audit will be implemented. Audit findings will be used to identify and correct problems.

**11.7 Web Based System.** Because the DCU uses a web-based system, source documents and CRFs will remain at the study site. This study database only identifies study subjects by unique study identification codes. All data will be stored in a manner that is HIPAA compliant, without the ability to track the information back to a specific subject except through a password protected system. All collected information about a subject will be stored by a unique identification code. All DCU personnel have completed human subject protection training and good clinical practice training.

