## **4.0 Study Endpoints**

### **4.1 Pilot primary outcome**

The primary efficacy outcome for this pilot study will be average daily pain from the electronic diaries during the 14-day period preceding the 90-day assessment, compared to the average daily pain reported during the 14-day run-in. Clinical improvement will be defined by the change in the average pain score between these two intervals, and without the need for increased opioids or additional interventions/procedures. A standardized 11-point Numeric Rating Scale (NRS) will be used to capture average daily pain with the empirically-supported anchors of 0=No Pain and 10=Worst Pain Imaginable.

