### 5.1 Inclusion Criteria

- Age  $\geq$  18 years
- Main pancreatic duct obstruction, defined by the presence of one or both of the following features:
  - Main pancreatic duct calcification with upstream main duct dilation  $\geq$  6mm.
  - Main pancreatic duct stricture, defined by the presence of main pancreatic duct narrowing with upstream main duct dilation  $\geq$  6mm.
- Baseline average abdominal pain score  $\geq$  4 during the run-in period, based on Ecological Momentary Assessment 11-point Numeric Rating Scale
- Ability to provide written, informed consent

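### The primary analysis uses a change from run-in pain, but section 11.4 names no estimator for it and does not commit to adjusting for run-in pain

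*Combined protocol and SAP*

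**What the plan says.** Section 4.1 takes mean diary pain in the 14 days before the 90-day assessment and compares it with mean diary pain in the 14-day run-in: "Clinical improvement will be defined by the change in the average pain score between these two intervals". It adds a condition, "and without the need for increased opioids or additional interventions/procedures". For subjects referred for another intervention before day 90, section 10.1.3 restarts the diary to "capture pain data for up to 14 days leading up to and including the day of intervention, as feasible", and the trial will "use these data to calculate the change score for the primary analysis". The same section says that a decision to intervene is not part of the pilot primary outcome.

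Section 11.4 has three sentences. The first gives analysis by assigned treatment. The second reads "Several exploratory analyses and descriptive statistics will be examined, including covariates". The third says that secondary outcomes "will be approached in a similar manner and considered exploratory using confident intervals rather than p values". No estimator, model or confidence level is given for the primary change score, and no covariate is named. Table 2 lists diary average daily pain in the column for potential covariates. Section 2.5 calls depression, opioid misuse, quality of life and catastrophizing important covariates. Neither commits to an adjustment.

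**The concern.** Two defensible analyses fit this text: a plain comparison of mean change, and a comparison of change adjusted for run-in pain. They can give different estimates from the same 30 subjects, and the plan does not say which is primary, so the choice could be made after the data are seen.

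They differ because subtracting the run-in value corrects fully for baseline only if day-90 pain rises one point for each point of run-in pain. If the slope is below 1, the arm that happens to start with more pain shows a larger average fall whatever the treatment does. With 15 per arm and no stratification on run-in pain described, some imbalance is expected. Section 15.2 expects the results to supply preliminary data for planning a definitive trial, so the estimate and its interval will be used. The secondary outcomes are tied to the primary method, so the gap carries over to them.

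**Working it through.** The plan has no figure to reproduce here. Section 11.2 supports 30 subjects by recruitment only (30 in 21 months is 30/21 × 12 = 17.1 per year, against 22 per year at one centre) and gives no SD, correlation, effect size or power.

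**Direction of the shift.** Write day-90 pain as a + τ·arm + b·(run-in) + error. Then change = a + τ·arm − (1 − b)·(run-in) + error. If the arms differ by D in mean run-in pain, the unadjusted difference in change has conditional expectation τ − (1 − b)·D. Over randomization D averages zero, so there is no bias overall. In a given trial the shift is (1 − b)·D, opposite in sign to D. A fall in pain is a good result, so the arm with more run-in pain looks better. Including run-in pain in the model removes this term.

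**Inputs.** From the documents: 15 per arm (11.2) and run-in mean of at least 4 (5.1). The only related pain figure is mean 4.8, SD 2.8, for a single BPI item in another cohort (2.5). Assumed: run-in pain normal with mean 4.8 and SD 2.8 or 2.0, cut to 4–10; day-90 pain with slope b and residual SD equal to SD × √(1 − b²); no treatment effect. Each setting was simulated 100,000 times.

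**Scenarios with the entry cut.** SD 2.8 leaves a run-in SD of 1.52 after the cut, so the standard error of the imbalance is 1.52 × √(2/15) ≈ 0.56. SD 2.0 leaves 1.30, giving 0.47. The shift is (1 − b) times that standard error. The half-width is the mean for unadjusted change.

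| Slope b | SD 2.8: shift / half-width | Estimates differ by > 0.5 | SD 2.0: shift / half-width | Estimates differ by > 0.5 |
|---|---|---|---|---|
| 0.4 | 0.33 / 2.02 = 17% | 16% | 0.28 / 1.48 = 19% | 11% |
| 0.5 | 0.28 / 1.88 = 15% | 12% | 0.24 / 1.37 = 17% | 7% |
| 0.6 | 0.22 / 1.72 = 13% | 8% | 0.19 / 1.25 = 15% | 4% |
| 0.7 | 0.17 / 1.52 = 11% | 4% | 0.14 / 1.10 = 13% | 2% |
| 0.8 | 0.11 / 1.27 = 9% | 2% | 0.09 / 0.91 = 10% | 0.5% |

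**Equal-SD scenario.** With run-in and day-90 SDs both 1.5, the slope equals the correlation r and the standard error of the imbalance is 1.5 × √(2/15) = 0.55. For r = 0.3, 0.5, 0.7 the shifts are 0.38, 0.27 and 0.16 against half-widths of 1.32, 1.11 and 0.86, which is 29%, 25% and 19%. The two estimates differ by more than 0.5 points in 19%, 9% and 2% of trials.

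**Precision.** The variance of the adjusted estimate relative to unadjusted change is σₑ² / [σₑ² + (1 − b)²·σₓ²] × (1 + 1/26). Here σₑ² is the residual variance, σₓ² the run-in variance after the cut, and the last factor the cost of estimating the slope.
- SD 2.8, b = 0.4: σₑ² = 7.84 × 0.84 = 6.59 and 0.36 × 1.52² = 0.83, so 6.59/7.42 × 1.038 = 0.92.
- SD 2.8, b = 0.8: 2.82/2.91 × 1.038 ≈ 1.00.
- SD 2.8, b = 0.9: 1.49/1.51 × 1.038 ≈ 1.02. Simulation gives 1.02–1.03, a small loss.
- SD 2.0, b = 0.4 to 0.8: 0.88 to 0.99 by simulation.
- Equal SDs: the ratio reduces to (1 + r)/2 × 1.038, or 0.68, 0.78 and 0.88 at r = 0.3, 0.5 and 0.7.

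**The case against.** The strongest reply is that this hardly matters in a pilot. Aim 1 is feasibility of recruitment, retention and blinding; Aim 2 is the choice of outcomes; no test is powered. In the scenarios with the entry cut at SD 2.8, adjustment narrows the half-width from 2.02 to 1.94 at best and not at all at slope 0.8. The two 95% intervals disagree on excluding zero in only 2–4% of simulated null trials. All of that stands and sets the weight. It does not remove the point, because section 4.1 names a primary efficacy outcome and section 11.4 leaves its estimator open.

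Section 11.4 is also not empty: it gives intention-to-treat, mentions covariates and prefers confidence intervals. A reader might infer that the plan has no approach at all, or that it has rejected baseline adjustment. The text supports neither. Adjustment is contemplated but not committed to.

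The opioid and procedure condition in section 4.1 makes the outcome less clear there than in section 10.1.3. A reader might conclude that the primary variable itself is undecided. Section 10.1.3 answers this for the analysis: it uses a change score and leaves the decision to intervene out of the pilot primary outcome.

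Finally, the proposed model does not deal with missing day-76–90 diaries, and it applies one slope to early pre-intervention windows and day-90 windows alike. Both limits are real and remain after the change.

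**Conclusion.** The point holds at low weight. The plan commits to a change score from run-in but states no primary estimator and no adjustment for run-in pain. A better method is available from data that the trial already collects.

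Under the assumed inputs, a one-standard-error run-in imbalance moves the unadjusted estimate by 9–19% of the 95% half-width with the entry cut and slopes of 0.4–0.8, and by 19–29% with equal SDs and correlations of 0.3–0.7. The variance ratio runs from about 0.68 to 1.00, with a loss of about 2–3% at slope 0.9. None of these sizes can be confirmed from the documents, because they contain no SD, slope or correlation for 14-day diary means.

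A reader might go further and call the unadjusted change biased or invalid. That is not supported: it is unbiased over randomization, and the shift exists only conditionally on the imbalance that occurs. Nor do the figures show that the trial's conclusion would usually turn on the choice.

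**What to change.** Add to section 11.4 wording such as:

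> The primary estimate is the treatment coefficient, with 95% confidence interval, from a linear model of the change in mean diary NRS on assigned treatment and run-in mean NRS. For a subject who has a re-intervention before day 90, the follow-up mean comes from the pre-intervention window in section 10.1.3. Unadjusted mean changes by arm are reported descriptively. The numbers with increased opioids or with additional procedures (section 4.1) are reported separately by arm.

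Reporting those numbers separately agrees with section 10.1.3, which keeps the decision to intervene out of the pilot primary outcome. The change score can stay: modelling change or follow-up pain on arm and run-in pain gives the same treatment coefficient. Use the same form, change on treatment plus the outcome's own baseline, for exploratory outcomes that have a baseline value, so that the reference to a similar manner points to a stated method.

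The cost is SAP wording and one degree of freedom (28 to 27). No new data are needed, because entry depends on average pain "during the run-in period, based on Ecological Momentary Assessment 11-point Numeric Rating Scale", so every randomized subject should have a run-in mean. If the slope is about 0.8 or higher, there is no gain in precision or a very small loss.
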